**Table 5 Protocol Required Safety Laboratory Assessments**

Laboratory Assessments	Parameters			
Haematology	Platelet Count	RBC Indices:	WBC count with Differential:	
	RBC Count	MCV	Neutrophils	
	Hemoglobin	MCH	Lymphocytes	
	Hematocrit		Monocytes	
			Eosinophils	
			Basophils	
Clinical Chemistry 	BUN	Potassium	AST (SGOT)	Total and direct bilirubin
	Creatinine	Sodium	ALT (SGPT)	Total Protein
	Glucose	Calcium	Alkaline phosphatase	Albumin
Other Screening Tests	
 
Hepatitis B (HBsAg)
 
Hepatitis C (Hep C antibody)
 
FSH and estradiol (as needed in women of non-child bearing potential only)
 
Alcohol and drug screen (to include at minimum: amphetamines, barbiturates, cocaine, opiates, cannabinoids and benzodiazepines)
 
Urine hCG Pregnancy test (as needed for women of child bearing potential)
 
			

**NOTES :**

1. Details of Liver Chemistry Stopping Criteria and Required Actions and Follow-Up Assessments after liver stopping or monitoring event are given in Section [5.5.3](#) and [Appendix 5](#)
2. Local urine testing will be standard for the protocol unless serum testing is required by local regulation or ethics committee.

All laboratory tests with values that are considered clinically significantly abnormal during participation in the study should be repeated until the values return to normal or baseline. If such values do not return to normal within a period judged reasonable by the investigator, the etiology should be identified and the sponsor notified.

#### **7.4.8. Paper worksheet**

Subjects will be issued with a paper worksheet to record adverse events, changes in concomitant medications and any visits to general practitioner, hospital and/or emergency department during the study. Subjects will be asked to bring their worksheet to every study site visit as it will be used to assist subject recall in discussions with the investigator, for site staff to then enter as appropriate in the eCRF.

#### **7.5. Biomarker(s)/Pharmacodynamic Markers**

Blood eosinophil counts will be recorded as part of the standard haematological assessments performed at the visits specified in the Time and Events Schedule (Section [7.1](#)). Additional blood samples for exploratory biomarkers of type 2 helper T cells (Th2) response, will be collected at Visits 1, 2, 4 and 10. Details on collecting and handling of biomarker samples can be found in the SRM.

#### **7.6. Immunogenicity**

Blood samples will be collected for the determination of anti-mepolizumab antibodies, prior to dosing, as detailed in the Time and Events Schedule (Section [7.1](#))

Details for sample collection and processing may be found in the SRM.

#### **7.7. Genetics**

Information regarding genetic research is included in [Appendix 14](#). IEC/IRB and, where required, the applicable regulatory agency must approve the genetic assessments before these can be conducted at the site. The approval(s) must be in writing and will clearly specify approval of the genetic assessments (i.e., approval of [Appendix 3](#)). In some cases, approval of the genetic assessments can occur after approval is obtained for the rest of the study. If so, then the written approval will clearly indicate approval of the genetic assessments is being deferred and the study, except for PGx and genetic assessments, can

be initiated. When genetic assessments will not be approved, then the approval for the rest of the study will clearly indicate this and therefore, genetic assessments will not be conducted

## 8. DATA MANAGEMENT

- For this study subject data will be entered into GSK defined CRFs, transmitted electronically to GSK or designee and combined with data provided from other sources in a validated data system.
- Management of clinical data will be performed in accordance with applicable GSK standards and data cleaning procedures to ensure the integrity of the data, e.g., removing errors and inconsistencies in the data.
- Adverse events and concomitant medications terms will be coded using Medical Dictionary for Regulatory Activities (MedDRA) and an internal validated medication dictionary, GSKDrug.
- CRFs (including queries and audit trails) will be retained by GSK, and copies will be sent to the investigator to maintain as the investigator copy. Subject initials will not be collected or transmitted to GSK according to GSK policy.

## 9. STATISTICAL CONSIDERATIONS AND DATA ANALYSES

### 9.1. Hypotheses

This study is designed to investigate whether subjects not optimally controlled on omalizumab can be effectively and safely switched to treatment with mepolizumab to improve asthma control. As there is no control arm in this study, comparisons in ACQ score will be made back to baseline.

### 9.2. Sample Size Considerations

#### 9.2.1. Sample Size Assumptions

The primary analysis will utilise within-subject changes from baseline. As this study is uncontrolled, the potential of a 'placebo effect' within the mepolizumab treated subjects will be considered. A meta-analysis of two previous severe asthma studies with mepolizumab (MEA115588 and MEA112997) estimated a change from baseline at Week 32 of -0.55 and -0.88 in the placebo and mepolizumab groups respectively, with mepolizumab presenting a benefit of -0.34 over placebo.

The following sample size estimates are based on a residual standard deviation of 0.96 units and are based upon the aforementioned meta-analysis. These estimates assume that 15% of subjects will prematurely withdraw from the study and therefore have missing

data at Week 32. This primary analysis will use the “missing at random” assumption for missing data.

With a sample size of 120 treated subjects, it is estimated that this study has over 90% power to detect a statistically significant improvement from baseline. Further it is estimated that a significant improvement over the ‘placebo effect’ of -0.55 from baseline in ACQ score will be observed at the two-sided 5% level of significance if the observed change from baseline is at least -0.74 units.

If the true change from baseline is -0.86 units, then the study has a probability of 90% of observing a change from baseline of at least -0.74 units and therefore the study has 90% power for declaring statistical significance over the ‘placebo effect’.

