**Table 6 Power for various changes from baseline and standard deviations**

Mean change from Baseline	Standard deviation				
	0.85	0.90	0.95	1.00	1.05
-0.75	65%	60%	56%	52%	48%
-0.80	84%	79%	75%	71%	66%
-0.85	94%	92%	88%	85%	82%
-0.90	98%	97%	96%	94%	92%
-0.95	>99%	99%	99%	98%	97%
-1.00	>99%	>99%	>99%	99%	99%

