2.4. Statistical Hypotheses

This study is designed to investigate whether subjects not optimally controlled on omalizumab can be effectively and safely switched to treatment with mepolizumab to improve asthma control. As there is no control arm in this study, comparisons in ACQ-5 score will be made to baseline. The first hypothesis to be tested will be for superiority of mepolizumab 100 mg SC treatment vs. baseline.

The potential of a ‘placebo effect’ within the mepolizumab treated subjects has been considered. In the protocol this was estimated as an improvement of -0.55 (SE: 0.05) from baseline in ACQ-5 score, based on the placebo effect observed in mepolizumab subjects from Phase 3 severe asthma studies (meta-analysis of double-blind studies MEA112997 and MEA115588). Improvements from baseline in ACQ-5 score will be assessed against this historical ‘placebo effect’. For further information regarding this historical ‘placebo effect’ please refer to Section 7.1.3.

Significance tests will be performed at the two-sided 5% alpha level (one-sided 2.5%).

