7. PRIMARY STATISTICAL ANALYSES

7.1. Efficacy Analyses

7.1.1. Overview of Planned Efficacy Analyses

The primary efficacy analyses will be based on the Intent-To-Treat (ITT) population. Additional sensitivity analysis will be performed on the Per Protocol population.

Table 4 provides an overview of the planned efficacy analyses, with full details of data displays being presented in [Appendix 13: List of Data Displays](#).

Table 4 Overview of Planned Efficacy Analyses

Endpoint	Absolute ^[1]								Change from Baseline ^[1]							
	Stats Analysis			Summary		Individual			Stats Analysis			Summary		Individual		
	T	F	L	T	F	F	L	T	F	L	T	F	F	L	T	F
Primary Endpoint																
Asthma Control Questionnaire (ACQ-5)																
On-treatment & Off-treatment ^{[2] [3]}	Y ^[4]				Y				Y ^[4]	Y ^[5]		Y	Y		Y	

NOTES :

- T = Table, F = Figure, L = Listing, Y = Yes display generated.
- Stats Analysis = Represents TFL related to any formal statistical analyses (i.e. modelling) conducted.
- Summary = Represents TFL related to any summaries (i.e. descriptive statistics) of the observed raw data.
- Individual = Represents FL related to any displays of individual subject observed raw data.

1. Absolute and change from baseline summaries combined into a single display.
2. To be generated for Intent-To-Treat (ITT) population and Per-Protocol (PP) population.
3. Subgroup analyses to be repeated for Intent-To-Treat (ITT) population and all subgroups listed within Section [10.10.2](#).
4. Table to include both Least Square Means and Least Square Mean Changes and estimated treatment difference (Mepolizumab-Historical Placebo) and 95% confidence interval at each visit from Mixed Model Repeated Measures (MMRM) Analysis.
5. Figure to present Least Square Mean Changes and corresponding 95% confidence intervals at each visit from MMRM Analysis

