7.1.2. Planned Efficacy Statistical Analyses

Primary Statistical Analyses
Endpoint(s)

 Mean change from baseline in ACQ-5 score at Week 32 (ADaM Dataset : ADACQ5)
Model Specification

 Endpoint will be analysed using a mixed models repeated measures (MMRM) analysis Dependent variable will be ACQ-5 score at each visit including the baseline Terms fitted in the MMRM analysis will include: Fixed Categorical Covariates : Region, Baseline maintenance OCS use, Visit Fixed Continuous Covariates : Exacerbations in the year prior to study (as an ordinal variable), Repeated : Visit See Section 10.10.1 for further details around model covariates.
Model Checking & Diagnostics

 Refer to Appendix 11: Model Checking and Diagnostics for Statistical Analyses.
Model Results Presentation

 Adjusted means and the corresponding 95% confidence intervals will be presented by visit. The estimated adjusted means will be presented using the observed marginal distribution of the sample covariates (OM option in LSMEANS statement). The Kenward and Roger method for approximating the denominator degrees of freedom and correcting for bias in the estimated variance-covariance of the fixed effects will be used (DDMF=KR). An unstructured covariance structure for the R matrix will be used by specifying 'type=UN' on the REPEATED line. Change from the baseline at each Visit X will be calculated by (Estimated Score at Visit X minus Estimated Score at Baseline) and the corresponding 95% confidence intervals. Adjusted means at each visit will also be presented. Plots of LS means change from baseline in ACQ-5 Score and 95% confidence intervals from the model will be generated by visit. Adjusted mean and corresponding standard error of mean will be presented, together with estimated between treatment difference (Mepolizumab – Historical Placebo) and the corresponding 95% confidence intervals at Week 32.
Treatment Phase

 All subjects in the ITT population will be included within this analysis. All data collected up to and including Week 32 from patients, including those who have discontinued study treatment, will be included in the analysis.
Sensitivity and Supportive Statistical Analyses

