
 Additional comparisons to historical placebo effect will be presented at Week 32 (refer to Section 7.1.3 for more details). A supporting sensitivity analysis of the Per Protocol (PP) population will also be performed. Subgroup analyses of the primary endpoint will be performed for all subgroups listed within Section 10.10.2.

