7.1.3. Analysis Comparing Against A Historical Placebo Effect

We will perform two separate analyses of the primary endpoint comparing to a historical 'placebo effect'.

[figure not shown]
Firstly, as specified in the protocol, a meta-analysis of previous exacerbation double-blind studies, MEA112997 and MEA115588, gave an estimate of -0.55 (SE: 0.05), for the improvement in the ACQ-5 score for placebo subjects at Week 32 compared to baseline. The observed improvement in this study for following mepolizumab treatment will be compared to this historical improvement on placebo.

Secondly, a meta-analysis has been performed of subjects within studies MEA115588 and 200862 who reported previous Xolair use, which may represent a more comparable population for this study. Study 200862 has completed since the protocol was finalised and previous Xolair usage was not collected in study MEA112997.

At Week 32 an estimate of -0.29 (SE: 0.248) was reported in the MEA115588 study while at Week 24 study 200862 reported an estimate of -0.03 (SE: 0.164) for the improvement in the ACQ-5 score for placebo subjects who previously used Xolair.

Weighted meta-analysis was performed on these values to get the combined estimate of -0.11 (SE: 0.14) for the historical placebo effect (Figure 1). This shows a reduction in the ACQ-5 score, but not as large as that specified in the protocol. The observed improvement in this study for mepolizumab vs. baseline will be also compared to this historical improvement on placebo.

Figure 1 Meta-analysis of ACQ-5 Placebo Effect in Previous Xolair Users

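### The -0.74 threshold, 90% power and Table 6 treat the historical -0.55 as error-free, while the SAP gives it SE 0.05 and does not say whether that SE enters the planned confidence interval

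*Protocol*

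**What the plan says.** Protocol section 9.2.1 (repeated in the Synopsis) takes the -0.55 from a meta-analysis of two earlier mepolizumab trials. It states that a significant improvement over that value "will be observed at the two-sided 5% level of significance if the observed change from baseline is at least -0.74 units". It then says that a true change of -0.86 gives a 90% chance of reaching this threshold, and "therefore the study has 90% power for declaring statistical significance over the" 'placebo effect'. Table 6, headed "Power for various changes from baseline and standard deviations", varies only the mean change and the SD. No uncertainty is attached to -0.55 anywhere in the protocol.

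The SAP treats the same number as an estimate. Section 2.4: "In the protocol this was estimated as an improvement of -0.55 (SE: 0.05) from baseline in ACQ-5 score". Section 7.1.3 says the meta-analysis "gave an estimate of -0.55 (SE: 0.05), for the improvement in the ACQ-5 score for placebo subjects at Week 32 compared to baseline", and adds a second benchmark for previous Xolair users of -0.11 with SE 0.14.

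The SAP then plans a difference between the two. Table 4, note 4, lists the "estimated treatment difference (Mepolizumab-Historical Placebo) and 95% confidence interval at each visit from Mixed Model Repeated Measures (MMRM) Analysis". Section 7.1.2 asks for the same difference ("Mepolizumab – Historical Placebo) and the corresponding 95% confidence intervals at Week 32") and, under sensitivity and supportive analyses, says that "Additional comparisons to historical placebo effect will be presented at Week 32". Neither 7.1.2 nor 7.1.3 gives a variance for the difference.

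**The concern.** The protocol and the SAP imply different tests. A test against a fixed number has only this trial's sampling error. A difference between this trial's mean and a historical estimate has both errors, so its standard error is larger and its power lower. The threshold, the 90% and Table 6 all belong to the first test. The SAP describes something that looks like the second.

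The SAP wording also allows an interval that is too narrow. Note 4 says the CI comes from the MMRM. That model is fitted to this trial's single mepolizumab arm and contains no historical variance. A programmer who follows it literally would subtract a constant from the MMRM estimate and carry its CI across unchanged. The effect is largest for -0.11, whose SE of 0.14 exceeds the trial's own expected SE of about 0.095. Section 7.1.3 suggests that this benchmark may come from the more comparable population, so readers may give it weight.

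In an uncontrolled trial, this comparison is the plan's own way of separating the drug effect from a placebo response.

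**Working it through.** **Inputs.** Protocol 9.2.1: 120 treated, 15% withdrawal, residual SD 0.96, benchmark -0.55, true change -0.86, two-sided 5%. SAP 2.4 and 7.1.3: SE 0.05 for -0.55. SAP 7.1.3: -0.11 with SE 0.14. The historical estimates are taken as independent of this trial and approximately normal.

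**1. Reproduce the protocol with -0.55 fixed.**

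- n = 120 × 0.85 = 102; SE_mepo = 0.96/√102 = 0.0951.
- Threshold = -0.55 - 1.96 × 0.0951 = -0.736 (normal), or -0.739 (t, 101 df). Both round to -0.74.
- Power at -0.86 = Φ(0.31/0.0951 - 1.96) = 90.3% (normal), or 89.8% (noncentral t).
- Probability of observing -0.74 or better at -0.86 = Φ(0.12/0.0951) = 89.7%.
- The noncentral t with 101 df reproduces all 30 cells of Table 6 to rounding. For example, -0.85 with SD 0.95 gives 88.5% (88.47%), printed as 88%.

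The arithmetic is right for a fixed benchmark, and Table 6 is power over -0.55.

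**2. Include SE 0.05.**

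- SE of the difference = √(0.0951² + 0.05²) = 0.1074.
- Threshold = -0.55 - 1.96 × 0.1074 = -0.761.
- The CI half-width rises from 0.186 to 0.211.

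Power depends on how the error in -0.55 is viewed. Reading A counts it as sampling error in both estimates: Φ((true-change distance from -0.761)/0.1074). Reading B takes -0.55 as already observed, so only this trial's mean varies: the same distance divided by 0.0951.

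| True change | -0.55 fixed | Reading A | Reading B |
|---|---|---|---|
| -0.86 | 90.3% | 82.3% | 85.2% |
| -0.88 (the meta-analysis value) | 93.5% | 86.7% | 89.6% |
| -0.85, SD 0.95 (Table 6 prints 88%) | 88.5% (t) | 80.4% | 83.4% |

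For 90% power the true change must be about -0.90 (A) or -0.88 (B). The SE of 0.05 is itself rounded: over 0.045 to 0.055, reading A at -0.86 runs from 83.8% to 80.6%.

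**3. Leave the SE out of the analysis.** The two-sided error rate, allowing for error in the benchmark, is 2 × [1 - Φ(1.96 × SE_mepo/SE_diff)].

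- Against -0.55: 1.96 × 0.0951/0.1074 gives 8.3% (7.7% at the rounded cut-off of -0.74).
- Against -0.11: SE_diff = √(0.0951² + 0.14²) = 0.1692, giving 27.1%. The cut-off would be -0.30 instead of -0.44, and the half-width 0.186 instead of 0.332.
- With the SE included, power against -0.11 at -0.86 is still 99%.

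**The case against.** The strongest reply is that testing a single arm against a fixed historical value is a recognised design. The protocol's calculation is correct for it, and the SE of 0.05 appears only in the later SAP. The comparison is also supportive. The SAP's first hypothesis is superiority over baseline, where power at -0.86 is above 99%. The threshold moves by only 0.02 ACQ units, and at -0.88 reading B still gives about 90%. The 8% and 27% rates arise only if an analyst omits the SE, which no text instructs outright. Printing an SE beside each benchmark may suggest the opposite, note 4 may be only a list of table contents, and the table shells are held in separate documents.

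Most of this stands, and it limits the size of the point. It does not remove it. A fixed benchmark is legitimate if declared, and it is not declared. Under one reading the advertised power does not apply to the reported difference. Under the other the interval is too narrow for a difference between two estimates. SAP Table 1, which lists changes from the protocol analysis, does not address this.

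**Conclusion.** The concern holds. The threshold of -0.74, the 90% power and every cell of Table 6 depend on treating -0.55 as error-free. For the difference between two estimates, the threshold is about -0.76 and power at -0.86 is about 82%, or 85% with -0.55 taken as observed. If the CI is taken directly from the MMRM, the two-sided error rate is about 8% against -0.55 and 27% against -0.11.

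These figures assume an SE of 0.0951 from the protocol's SD and 102 evaluable subjects; the SE from the SAP's MMRM may differ. The primary comparison with baseline and the adequacy of the sample size for it are not in question. No threshold or power is stated for -0.11, so no printed figure is wrong there; only the interval construction is open. The choice would decide how an observed change between -0.74 and -0.76, or between -0.30 and -0.44, is described.

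**What to change.** 1. In SAP 7.1.2 and 7.1.3, and in Table 4 note 4, state that the CI and test for mepolizumab minus historical placebo use √(SE_mepo² + SE_hist²), with SE_hist of 0.05 for -0.55 and 0.14 for -0.11. Settle this before database freeze.
2. Wherever the sizing is reported, restate the threshold as about -0.76 and power at -0.86 as about 82% (85% with -0.55 taken as observed), and recompute Table 6. Alternatively, keep the existing threshold, power and table and label them as conditional on a fixed -0.55.

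The cost is one SAP sentence, carried into note 4, and restated or labelled figures. No further subjects are needed and the test against baseline does not change. The price is wider intervals, slightly so for -0.55 and clearly so for -0.11, and, if the figures are restated, a lower stated power.

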### 9.2.2. Sample Size Sensitivity

If either the actual change from baseline or variability are different from the values assumed in Section 9.2.1, the power to detect a change in ACQ score will be affected.

**Table 6** illustrates the estimated power which would be obtained with different values of change from baseline and standard deviation, assuming 120 patients are treated.

**Table 6 Power for various changes from baseline and standard deviations**

Mean change from Baseline	Standard deviation				
	0.85	0.90	0.95	1.00	1.05
-0.75	65%	60%	56%	52%	48%
-0.80	84%	79%	75%	71%	66%
-0.85	94%	92%	88%	85%	82%
-0.90	98%	97%	96%	94%	92%
-0.95	>99%	99%	99%	98%	97%
-1.00	>99%	>99%	>99%	99%	99%

## 9.3. Data Analysis Considerations

### 9.3.1. Analysis Populations

#### All Subjects Enrolled (ASE) Population

The ASE population will comprise all subjects enrolled and for whom a record exists on the study database. This population will be used for summarising reasons for screen and run-in failures.

#### Intent-to-Treat (ITT) Population

This population will consist of all subjects who receive at least one dose of mepolizumab, and will be the primary population for all analyses of efficacy measures and safety measures.

### **Per Protocol (PP) Population**

The Per Protocol (PP) population will consist of all subjects in the Intent-to-Treat population who have not been identified as full protocol deviators with respect to criteria that are considered to impact the primary efficacy analysis. The decision to exclude a subject from the PP population or exclude part of their data from the PP population analyses will be made prior to freezing the study database. The PP population will be used for a supplementary analysis of the primary endpoint.

#### **9.3.2. Interim Analysis**

No interim analysis is planned for this study.

### **9.4. Key Elements of Analysis Plan**

All pre-specified analyses will be described in a full Reporting and Analysis Plan (RAP) which will be finalised prior to freezing the study database. Any changes to what is detailed in the protocol will also be described in the RAP.

The study database will be frozen once the final subject has completed the Exit visit and all queries for data collected up to this time are resolved.

